**Listing 16.2.1.3 Patient Visits – Enrolled Set**

All patient visits and visit dates and the respective study day will be listed by patient.

**Listing 16.2.1.4 Exclusions from Analysis Sets – Randomised Set**

Patients excluded from the safety, full analysis and per-protocol set and corresponding reasons for exclusion will be listed.

**Listing 16.2.1.5 Patient Randomisation to Treatments – Randomised Set**

Randomisation numbers and treatment assignments will be listed for all randomised patients.

## **5.1.2 Protocol Deviations**

Protocol deviations are deviations from the procedures outlined in the clinical study protocol or from subsequent protocol-related instructions like missed evaluations, incorrect timing of evaluations, non-compliance with IMP and intake of prohibited medications or any non-adherence to the clinical study protocol that impacts patient's rights, safety or welfare.

Major protocol deviations will be summarised. Protocol deviations (including COVID-19 pandemic related protocol deviations) will be evaluated as major or minor during BDR (See Section 6).

Patients will be excluded from the PPS for the following reasons:

- No acute intracerebral haemorrhage or acute ischaemic stroke confirmed by Magnetic resonance imaging (MRI)/ Computed tomography (CT).
- First administration of IMP was more than 96/120 hours after stroke occurrence respective to the protocol version, or since last time seen well.
- Brain scanning has not excluded structural brain lesions that can mimic stroke, e.g. cerebral tumor or brain abscess, etc.

- Use of prohibited medication or treatments
- Other events occur that may have a relevant impact on the efficacy evaluations. Such trial conditions, which may or may not represent a protocol deviation or violation, will be identified during the data review meeting.

COVID-19 pandemic related protocol deviations will be taken from Global-PD-Log (PD category 13: COVID-19 pandemic).

The following statistical outputs will be provided:

**Table 15.1.5.1 Major Protocol Deviations – Safety Set**

The number and percentage of patients with major protocol deviations will be summarised by treatment group and in total. The categories of major protocol deviations will be included. Percentages will be based on the number of patients in the respective analysis set.

**Listing 16.2.1.6.1 Major Protocol Deviations – Safety Set**

Patients with major protocol deviations will be listed by treatment group.

**Listing 16.2.1.6.2 Protocol Deviations related to COVID-19 – Enrolled Set**

Minor and major deviations related to COVID-19 will be listed by patient by treatment group (ESL, placebo and Screening Failures).

**5.1.3 Inclusion/Exclusion**

For each inclusion/exclusion criterion, as appropriate, a response of “Yes/No” is to be obtained at V1a and V1b. Inclusion criteria at V2 are checked only for patients who were unable to give informed consent at V1a except for Portugal.

The following statistical output will be provided:

**Listing 16.2.1.7 Inclusion Criteria Not Met and Exclusion Criteria Met – Enrolled Set**

Inclusion criteria which were not met and exclusion criteria which were met will be listed by treatment group.

**5.2 Demographic and Other Baseline Characteristics**

**5.2.1 Demographics**

The following demographic characteristics will be presented:

- Age
- Year of birth
- Gender
- Childbearing potential (yes/no), if patient is female
- Race

The following statistical outputs will be presented:

**Table 15.1.6.1 Demographics – Safety Set**

**Table 15.1.6.2 Demographics – Per-Protocol Set**

Demographic data will be summarised for each treatment group and in total in the respective set. Overall summary will also be included. Percentage of females of childbearing potential will be based on the number of females while all other percentages will be based on the number of patients in the respective analysis set.

**Listing 16.2.1.8 Demographics– Enrolled Set**

Demographic data will be listed for patients in the enrolled set.

**5.2.2 Primary Stroke Characteristics**

Information concerning the primary stroke will be collected:

- mRS

- total NIHSS (worst score post-stroke until V1b)
- (Total) SeLECT/CAVE score
- Primary stroke and brain imaging details
- For acute ischemic stroke only: Development of a secondary haemorrhage details

The **Modified Rankin Scale (mRS)** is a single item, global outcomes rating scale which was designed to measure post-stroke recovery. However, in the present trial the scale is used to measure pre-stroke disability and confirm patient eligibility.

Modified Rankin Scale Description	Grade
No symptoms at all	0
No significant disability despite symptoms; able to carry out all usual duties and activities	1
Slight disability; unable to carry out all previous activities, but able to look after own affairs without assistance	2
Moderate disability; requiring some help, but able to walk without assistance	3
Moderately severe disability; unable to walk without assistance, and unable to attend to own bodily needs without assistance	4
Severe disability; bedridden, incontinent, and requiring constant nursing care and attention	5

The **National Institutes of Health Stroke Scale (NIHSS)** is a systematic assessment tool that provides a quantitative measure of stroke-related neurologic deficits (see also section 5.5.2.6 below). The worst total NIHSS score post-stroke until V1b will be collected.

To calculate the **CAVE score or SeLECT score**, brain scanning results (MRI/CT) will be used. The assessment will be performed at V2 (V1a in the CTP Final Version 2.0). In case V2 is scheduled earlier than 7 days post stroke the assessment of early seizures after stroke will be done at V3.

For patients included according to the CTP Final Version 2.0 or respective country-specific protocol versions, the **initial CAVE score** and **initial SeLECT score** were assessed by the investigators at V1a (less than 7 days after the primary stroke). Due to the fact that acute seizures can occur within 7 days after the primary stroke, the **total CAVE score or total SeLECT score** after 7 days could theoretically be higher than respective scores documented at V1a. It was confirmed (for patients included according to the CTP Final Version 2.0 or respective country-specific protocol versions) that no acute seizures have occurred after V1a. For patients with ischaemic stroke also the total worst NIHSS score was compared to NIHSS documented within the SeLECT score and total scoring was confirmed to be correct for all patients. The **total CAVE** and **total SeLECT** score are therefore identical to the initial scores for all patients and comparable to the scores collected for patients included according to the CTP Final Version 3.0 or respective country-specific protocol versions. A manual correction of the total CAVE or total SeLECT scores was therefore not applicable.

The **SeLECT score** was developed to calculate the patient's individual risks of having a seizure after an acute ischemic stroke. The patient's individual total SeLECT score will be calculated by adding the points associated with each predictor [4]:

Predictors of SeLECT Score:	Category	Points
(Se) Severity of stroke	NIHSS $\leq$ 3	0
	NIHSS 4 to 10	1
	NIHSS $\geq$ 11	2
(L) Large-artery atherosclerosis	No	0
	Yes	1
(E) Early seizure ( $\leq$ 7 days)	No	0
	Yes	3
(C) Cortical involvement	No	0
	Yes	2
(T) Territory of MCA	No	0
	Yes	1

The **CAVE score** was developed to calculate the patient's individual risks of having a seizure after intracerebral haemorrhage. To calculate an individual's CAVE score, the points associated with each predictor will be added to obtain the total risk score: [5].

Predictors of CAVE Score	Points
Cortical involvement of intracerebral haemorrhage	1
Age $<$ 65 years	1
Volume of intracerebral haemorrhage $>$ 10 mL	1
Early seizure within 7 days of intracerebral haemorrhage	1

The following **details for the primary stroke** will be collected:

- Date/time of primary stroke
- Type of primary stroke (acute intracerebral haemorrhagic stroke or acute ischaemic stroke)
- If type is acute intracerebral haemorrhagic stroke:
  - Cortical involvement of intracerebral haemorrhage (yes/no)
  - Age  $<$  65 years (yes/no)
  - Volume of intracerebral haemorrhage  $>$  10 mL (yes/no)
  - Early seizure within 7 days of intracerebral haemorrhage (yes/no)
  - CAVE Score
- If type is acute ischaemic stroke:
  - Severity of stroke (NIHSS  $\leq$  3, NIHSS 4 to 10, NIHSS  $\geq$  11)
  - Large-artery atherosclerosis (yes/no)
  - Early seizure ( $\leq$  7 days) (yes/no)
  - Cortical involvement (yes/no)
  - Territory of middle cerebral artery (MCA) (yes/no)
  - SeLECT Score
- mRS

The **brain imaging (MRI/CT) details** include:

- Type of procedure (MRI or CT)
- Date of procedure
- Scan conclusion

If the type of primary stroke is “acute ischaemic stroke”, the details about the **development of a secondary haemorrhage** will be collected:

- Development of a secondary haemorrhage (yes / no / unknown)
- If yes, then:
  - Date/time identified after primary acute ischaemic stroke
  - Volume of the haemorrhage  $>$  10mL (yes/no)
  - Involvement of the cerebral cortex, even if the origin of the bleeding was in deep structures (yes/no)

The following statistical outputs will be provided:

Table 15.1.7.1 Summary of Primary Stroke Characteristics – Safety Set

Table 15.1.7.2 Summary of Primary Stroke Characteristics – Per-Protocol Set

Primary Stoke characteristics will be summarised for the SS, FAS and PPS by treatment group and in total. Counts and percentages of patients by the type of stroke (acute ischaemic stroke or acute intracerebral haemorrhagic stroke) will be presented. Total SeLECT and total CAVE scores as well as mRS will be summarised by means of descriptive statistics. The number of patients that developed a secondary haemorrhage will be summarised.

Listing 16.2.1.9 (Primary) Stroke and Brain Imaging Details – Enrolled Set

Date, time and type of primary stroke, brain imaging details, worst total NIHSS and mRS will be listed for the ES by treatment group. Data about the development of a secondary haemorrhage will be included, if applicable.

Listing 16.2.1.10 SeLECT and CAVE Scores – Enrolled Set

Total SeLECT and CAVE scores will be listed by treatment group including points for each predictor and if a correction was necessary, type of stroke will be indicated for each patient.

### 5.2.3 Medical History

Medical history encompasses relevant (former 6 month) previous or ongoing relevant diseases, conditions, hospitalisation and surgical procedures except the primary stroke. Medical history records are collected at V1a. If the patient was unable to give informed consent at V1a, medical history is collected at V2.

A stroke occurring within 7 days after the primary stroke will be considered as re-stroke and documented in the medical history if occurred before patient enrolment.

Medical history of the patients includes:

- Diagnosis
- Start date
- Ongoing (yes/no)
- Stop date, if applicable
- Medication taken (at the time of patient's enrolment)? (yes/no)

Medical history is classified as:

- **Previous medical conditions** are the conditions which started and ended prior to V1a.
- **Ongoing medical conditions** are the conditions which are marked as ongoing at V1a or with a stop date at or after V1a.

If the stop date of a medical history condition is incomplete or missing, it will be assumed to be ongoing except if the incomplete stop date indicates that the condition stopped prior to the V1a.

The following statistical output will be provided:

Table 15.1.8.1.1 Previous Medical Conditions – Safety Set

Table 15.1.8.2.1 Ongoing Medical Conditions – Safety Set

Medical history except for the primary stroke will be summarised by treatment group and in total displaying counts and percentages of patients having at least one medical condition and will be presented by Primary System Organ Class (SOC) and by Preferred Term (PT) within SOC. SOCs and PT within SOC are to be sorted by descending order of overall incidence. Patients with two or more occurrences of the same condition (as qualified by its PTs) will be counted only once for the respective PT. Percentages will be based on the number of patients in the respective analysis set.

Listing 16.2.1.11 Medical History – Enrolled Set

Medical history conditions will be listed for patients in the enrolled set by treatment group.

### 5.3 Previous and Concomitant Medications and Therapies

The following information is documented about previous and concomitant medications and concomitant therapies in the eCRF:

- Medication / therapy name
- Indication
- Total Daily Dose
- Units
- Route
- Frequency
- Start date of medication/ therapy
- Ongoing (yes, no)
- Stop date of medication, if applicable

Total daily dose, units and route will be collected as NA for concomitant therapies.

Medications will be classified as ‘previous’, ‘concomitant’ or ‘post’ based on start/stop dates:

- **Previous medications** are defined as those medications starting and ending prior to the first IMP intake.
- **Concomitant medications** are defined as medications started at or after first IMP intake and at or before the last IMP intake. It also includes medications that started prior to the first IMP intake but continued after the first IMP intake.
- **Post-treatment [subsequent] medications** are defined as medications which started after the last IMP intake.
- **Therapies related to primary stroke** are defined as therapies (preferred terms) that are related to the primary stroke according to the indication provided by the investigator (primary stroke or related post-stroke rehabilitations). The indications of therapies were manually reviewed and evaluated by the Medical Monitor to select “Therapies related to primary stroke”.

If the start or stop date of a medication is incomplete or missing, it will be assumed to be concomitant except if the incomplete start or stop date indicates that the medication stopped prior to the first IMP intake or started after the last IMP intake.

The following statistical output will be provided:

Table 15.1.9.1 Previous Medications – Safety Set

Table 15.1.9.2 Concomitant Medications – Safety Set

The number and percentage of patients with at least one previous or concomitant medication within each ATC 2nd level subgroup and substance name (or combination of substances) will be presented by treatment and in total for the respective analysis set. The ATC 2nd level subgroups and substance names within ATC 2nd level subgroup will be ordered by descending overall incidence.

Table 15.1.9.3.1 Therapies Related to Primary Stroke – Safety Set

Table 15.1.9.3.2 Therapies Related to Primary Stroke – Per-Protocol Set

The number and percentage of patients with at least one therapy related to indication “primary stroke or related post-stroke rehabilitation” will be presented by therapy name (PT) and in total for the respective analysis set. The PT will be ordered by descending overall incidence.

Table 15.1.9.4.1 Concomitant Anti-Epileptic Drugs – Safety Set

Table 15.1.9.4.2 Concomitant Anti-Epileptic Drugs – Per-Protocol Set

Number and percentages of patients receiving Anti-epileptic drugs (AEDs) as concomitant therapy will be presented by treatment group and in total, including substance name, for the respective set.

#### **Listing 16.2.1.12 Medications – Enrolled Set**

All medications, previous, concomitant and post [subsequent], will be listed for patients in the enrolled set by treatment group. Anti-epileptic drugs will be marked.

#### **Listing 16.2.1.13 Therapies – Enrolled Set**

All therapies (all indications) will be listed for patients in the enrolled set by treatment group.

### **5.4 Exposure to IMP and Compliance**

#### **5.4.1 Exposure to IMP**

IMP will be taken from V1b (Day 1) to Day 30 by all patients. Patients taking once daily one tablet will take in addition half a tablet from Day 31 to Day 37.

At V3, patients will bring back their IMP bottle including all unused tablets and drug accountability will be performed.

Exposure data from eCRF include:

- Date and time of first IMP intake
- Prescribed dose of IMP (mg)
- Prescribed from (date)
- Prescribed until (date)
- This is tampering-off dose (tick)
- Reason for change
- Number of IMP tablets
- Date of last IMP intake
- Total number of IMP tablets patient should have taken according to prescription
- Bottle number of dispensed IMP
- Bottle number of returned IMP
- Number of tablets returned
- Reason of IMP accountability discrepancy.

The **treatment duration** (while on treatment) in days will be calculated as follows:

- treatment duration (days) = (date of last IMP intake – date of first IMP intake + 1) – (end date of interruption – start date of interruption +1)

The **total dose of IMP** taken will be calculated in tablets as follows:

Total dose (tablets)

$$= 40 \times \text{Number of bottles dispensed} - \text{Total number of IMP tablets returned}$$

Note: Each IMP bottle is a monthly pack containing 40 tablets.

The **mean daily dose of IMP** in mg will be calculated as follows:

$$\text{Mean daily dose (mg)} = \frac{\text{Total dose (tablets)} \times \text{Tablet strength}}{\text{Treatment duration (while on treatment) (days)}}$$

Note: Tablet strength for patients who received ESL will be 800 mg. For patients who received placebo the mean daily dose will not be available (n.a.).

The following statistical output will be provided:

#### **Table 15.1.10.1.1 Exposure to IMP – Safety Set**

#### **Table 15.1.10.1.2 Exposure to IMP – Per-Protocol Set**

The default summary statistics of treatment duration, total dose of IMP (tablets) and the mean daily dose (mg) will be presented by treatment group and overall. The prescribed number and percentages of tablets will be summarised. The number of patient with a treatment duration  $\leq 4$  days will be displayed.

#### **Listing 16.2.2.1 Exposure to IMP– Safety Set**

Exposure to treatment data will be displayed for each patient in the safety set.

#### **5.4.2 Compliance**

Overall treatment compliance will be calculated as:

$$\text{Overall compliance (\%)} = \frac{\text{Number of IMP tablets taken}}{\text{Number of IMP tablets the patient should have taken}} \times 100$$

The number of IMP tablets taken and the number of IMP tablets the patient should have taken will be collected in eCRF. The “Number of IMP tablets taken” will be calculated by “Dispensed Amount of Tablets” – “Returned Amount of Tablets”.

In case an IMP bottle is not returned, the overall compliance will be considered as missing.

All patients with a compliance <80% and >120% will be discussed at BDRM. It was decided during BDRM that all patients with a treatment duration > 4 days are compliant, as this is the very minimum amount of intakes to reach steady state serum level of ESL. Patients with missing compliance were discussed at BDRM and compliance was assessed on a case-by-case basis.

The following statistical output will be provided:

#### **Table 15.1.10.2.1 Treatment Compliance (%) – Safety Set**

#### **Table 15.1.10.2.2 Treatment Compliance (%) – Per-Protocol Set**

The default summary statistics of compliance will be presented by treatment group and overall. The number and percentage of patients within each compliance category (< 80%, ≥ 80% and ≤ 120%, >120%) will also be summarised. Percentages will be based on the number of patients in the corresponding analysis set.

#### **Listing 16.2.2.2 Treatment Duration and Compliance– Safety Set**

Treatment duration as well as the total dose of IMP, mean daily dose of IMP, planned total dose of IMP and overall compliance will be displayed for each patient in the safety set.

#### **Listing 16.2.2.3 IMP Accountability– Safety Set**

IMP accountability data will be displayed for each patient in the safety set.

### **5.5 Efficacy Analysis**

#### **5.5.1 Primary Efficacy Analysis**

The FAS and the PPS will be used for the analysis of the primary efficacy analysis.

The primary endpoint is the proportion of patients who experience the first US within the first 6 months (until Day 182) after randomisation (failure rate). First US within the first 6 month, deaths before the first US and patients without evaluable assessment of the primary endpoint will be counted as treatment failures. The first occurring event will be used for this analysis e.g. if a patient experiences an US and dies later, this patient will be included as a patient with an US. If a patient experienced a re-stroke, the patient will be counted as a withdrawal with the date of re-stroke as ‘Date of withdrawal’.

To show that ESL is different to placebo, the primary null hypothesis

$$H_0: p_{ESL} \geq p_{placebo}$$

will be tested against the alternative hypothesis

$$H_1: p_{ESL} < p_{placebo}$$

where  $p_{ESL}$  and  $p_{placebo}$  denote the proportions of patients with the first US within 6 months after randomisation in ESL and placebo patients, respectively.

The primary hypotheses will be assessed in the FAS by means of a chi-square test with continuity correction on the significance level of 5% (two-sided, which corresponds to the significance level of

2.5% one-sided). The Odds Ratio for Placebo vs. ESL and the corresponding 95% score CI will be provided. The Risk Difference (RD) of failing between Placebo and ESL with corresponding 95% continuity-corrected Newcombe Confidence Interval (CI) for the risk difference Placebo – ESL will be calculated. Additionally, the p-value of Fisher's exact test will be provided.

For this purpose, the following SAS code will be used:

**Note: Data should be sorted by descending treatment group (first “ESL” then “Placebo”) and by treatment failures (first “Failure” then “Non-failure”).**

```
PROC FREQ DATA = <dataset> order=data;
  TABLE <Treatment group> * < Treatment Failure>
    /CHISQ RISKDIFF (CL =Newcombe (Corrected)) OR(CL =SCORE) ALPHA=0.05;
RUN;

PROC FREQ DATA = <dataset> order=data;
  tables <Treatment group> * < Treatment Failure>/ fisher;
run;
```

The following statistical outputs will be created:

Table 15.2.1.1.1 Analysis of Treatment Failure Rate within 6 Months after Randomisation – Full Analysis Set

Table 15.2.1.1.2 Analysis of Treatment Failure Rate within 6 Months after Randomisation – Per-Protocol Set

Number and percentage of failures (overall, US, death, early withdrawal, missing) and non-failures 6 months after randomisation will be tabulated, including degrees of freedom (DF), value and p-value for chi-square test, p-value for Fisher's exact test, RD of failing between ESL and Placebo with corresponding 95% continuity-corrected Newcombe CI as well as ESL vs. PlaceboOR with 95% score confidence interval.

Listing 16.2.3.1 Seizure Screening Questionnaire – Enrolled Set

Seizure screening questionnaire data will be listed.

Listing 16.2.3.2 Seizure Information after the Primary Stroke Occurrence – Enrolled Set

Seizure information after the primary stroke occurrence will be listed.

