Objectives: Primary: To assess if eslicarbazepine acetate (ESL) treatment (started within 96 hours after stroke occurrence and continued for 30 days) changes the incidence of unprovoked seizures (USs) within the first 6 months after randomisation as compared to placebo. Secondary: 1. To assess if ESL treatment (started within 96 hours after stroke occurrence and continued for 30 days) changes the incidence of USs within the first 12 months after randomisation as compared to placebo 2. To assess if ESL treatment (started within 96 hours after stroke occurrence and continued for 30 days) changes the incidence of USs during the course of the trial - until 18 months after randomisation as compared to placebo 3. To assess the number of acute symptomatic seizures (ASs) To assess the effect of ESL treatment over 18 months follow-up period on: 4. Time to first US after randomisation 5. Time to first US after stroke occurrence 6. Number and 4-week rate of USs 7. Functional outcome, assessed by Barthel Index original 10-item version (BI) 8. Functional outcome, assessed by National Institutes of Health Stroke Scale (NIHSS) 9. Post-stroke depression, assessed by Patient Health Questionnaire (PHQ-9) 10. Overall survival	

Safety:

To assess the effect of ESL treatment on:

11. Treatment emergent adverse events (TEAEs) incl. findings from physical and neurological examinations
12. Laboratory parameters
13. Vital signs
14. Electrocardiogram (ECG)
15. Suicidal ideation and behaviour, assessed by PHQ-9 (question 9)

Exploratory:

16. Electroencephalogram (EEG), optional

Methods/trial design:

The following definitions will be applied for this trial:

Acute symptomatic seizure (AS): Epileptic seizure or status epilepticus (of any type) occurring within 7 days (\leq 7 days) after primary stroke.

Unprovoked seizure (US): Epileptic seizure or status epilepticus (of any type) occurring later than 7 days ($>$ 7 days) after primary stroke.

Re-stroke: If an additional stroke occurs within the first 7 days after the primary stroke, this will be considered as one stroke event and will not lead to withdrawal of the patient.

Post-stroke epilepsy: One unprovoked (or reflex) seizure with a probability of further seizures similar to the general recurrence risk (at least 60%) after 2 USs, occurring over the next 10 years.

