### **2.2 Study Endpoints**

#### **2.2.1 Primary Efficacy Endpoints**

The primary endpoint of this trial is the proportion of patients who experience the first US within the first 6 months after randomisation. Deaths before the first US or patients without evaluable assessment of the primary endpoint (i.e. drop-outs independently of the reason) will be counted as treatment failures (failure rate).

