### **5.5.1.1 Sensitivity Analyses**

For the primary analysis, patients withdrawing early during the trial will be considered as non-seizure free (treatment failure). This replacement strategy is defined under the assumption that it cannot be excluded that “missingness” is related to treatment failure and thus not at random. In order to assess the effect of missing data, the following sensitivity analyses will be performed:

The primary analysis will be repeated by imputing the missing values (patient withdrew from study before primary endpoint was reached) in both groups (ESL and Placebo) multiple times assuming the rate of treatment failures among the missing data follows the observed rate of treatment failures in the placebo group.

The following SAS code will be used:

**Note: Treatment Failure will be 1 if a patient had an US or died, 0 if not and ‘.’ if the data is missing (patient withdrew). A dummy baseline variable that consists only 0 will be created. Treatment group will be 1, if the patient received ESL and 2 if the patient received placebo. n will be the number of patients that experienced at least one US until 6 months.**

```
proc mi data=<data> seed=14823 nimpute=&n. out=<out> noint;
  class <Treatment group> <Treatment Failure>;
  var <Baseline Dummy> <Treatment Failure>;
  monotone logistic(<Treatment Failure> /detail);
  mnar model(<Treatment Failure> / modelobs=(trt='2'));
run;
```

The chi-square test as described in 5.5.1 will be applied to each of the imputed datasets. The results will be pooled by Rubin's rule. For the Odds Ratio, the logarithm will be applied before pooling and afterwards the exponential function will be applied:

```
DATA lgsodds_t;
  SET < DATA ODDS>;
  log_or_lr_value=LOG(ODDSRATIO);
  log_or_lr_se=(LOG(UPPERCL)-LOG(LOWERCL)) / (2*1.96);
RUN;
*** Combine transformed estimates;
PROC MIANALYZE DATA=lgsodds_t;
  ODS OUTPUT PARAMETERESTIMATES=mian_lgsodds_t;
  MODELEFFECTS log_or_lr_value;
  STDERR log_or_lr_se;
RUN;
*** Back-transform combined values;
DATA mian_lgsodds_bt; SET mian_lgsodds_t;
  Estimate_back = EXP(ESTIMATE); *Pooled odds ratio;
  LCL_back=Estimate_back*EXP(-1.96*STDERR); *Pooled lower limit;
  UCL_back=Estimate_back*EXP(+1.96*STDERR); *Pooled upper limit;
RUN;
```

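### The re-stroke rule in SAP 5.5.1 has no 7-day limit, so as written it can score a patient observed seizure-free to Day 182 as a failure (minor)

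*SAP*

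**What the plan says.** **The analysis rule.** SAP 5.5.1 states: "If a patient experienced a re-stroke, the patient will be counted as a withdrawal with the date of re-stroke as" the date of withdrawal. It gives no time window. The sentence before it says that the first event to occur decides the classification. The revision history shows that the rule entered in Draft 0.5, after sponsor review and the blind data review meeting.

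**What a withdrawal means.** SAP 2.2.1 counts patients without an evaluable primary endpoint as failures and explains these as "drop-outs independently of the reason". SAP 5.5.1.1 says the same of early withdrawals, because missingness may be related to failure. The primary output tabulates "Number and percentage of failures (overall, US, death, early withdrawal, missing) and non-failures 6 months after randomisation".

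**What a re-stroke is.** In the definitions of the protocol synopsis, a further stroke in the first 7 days after the primary stroke is covered thus: "this will be considered as one stroke event and will not lead to withdrawal of the patient". SAP 5.2.3 uses the same window: "A stroke occurring within 7 days after the primary stroke will be considered as re-stroke". It adds that such a stroke is "documented in the medical history if occurred before patient enrolment".

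**Where the rule carries.** SAP 5.5.2.1 applies the primary approach to the 12- and 18-month failure rates.

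**The concern.** The only meaning given to re-stroke in the supplied documents is a stroke within 7 days of the primary stroke. That is the group the protocol synopsis keeps in the trial. A programmer who combines SAP 5.2.3 with SAP 5.5.1 would therefore withdraw, and so fail, patients whom the protocol does not withdraw.

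Counting a withdrawal as a failure is justified in the SAP by a missing outcome. For a patient who stays in the trial after an early re-stroke and reaches Day 182 without a US, nothing is missing. The rule would replace an observed non-failure with a failure in the primary test.

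**Working it through.** **Step 1. Can the case arise?** The window is 7 × 24 = 168 hours. V1b is within 96 hours of stroke in the supplied protocol and within 120 hours in the SAP. At least 168 − 96 = 72 hours, or 168 − 120 = 48 hours, of the window therefore falls after V1b.

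**Step 2. Who is misclassified under the literal rule?**

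| Patient | Literal result at 6 months | Affected? |
|---|---|---|
| Re-stroke after randomisation, within 7 days; no US to Day 182 | Withdrawal, so failure | Yes: observed non-failure becomes failure |
| Same re-stroke, US later by Day 182 | Failure either way | Only the tabulated category changes |
| US first, re-stroke later | US (first event decides) | No |
| Re-stroke after Day 182 | Outside the 6-month period (SAP 4.7) | No |
| Re-stroke before enrolment | Recorded as medical history (SAP 5.2.3) | Probably not, but 5.5.1 is silent |

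On the last row, SAP 5.1.1 defines withdrawals as patients who discontinue after randomisation. That suggests these patients fall outside the rule.

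**Step 3. The sensitivity analyses.** For the multiple imputation, "Treatment Failure will be 1 if a patient had an US or died, 0 if not", with a missing code for a patient who withdrew. With the first-event rule, a patient whose early re-stroke precedes any US would be coded missing, and the observed outcome would be imputed. The tipping point analysis would vary that outcome. The US-only analysis would count a seizure-free patient as a non-failure. The last two could reveal an effect but do not change the primary test.

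**Step 4. The plan's own sample size.** Inputs from the protocol synopsis: failure rates 26% and 8%, 5% missing per arm counted as failures, continuity-corrected chi-square test, two-sided 5%, power 80%.
- Adjusted rates: 0.05 + 0.95 × 0.26 = 0.297; 0.05 + 0.95 × 0.08 = 0.126; difference d = 0.171.
- Uncorrected m = [1.960·√(2 × 0.2115 × 0.7885) + 0.842·√(0.297 × 0.703 + 0.126 × 0.874)]² / 0.171² ≈ 88.3, so 89 per arm.
- Corrected n = (m/4)·[1 + √(1 + 4/(m·d))]² ≈ 99.7, so 100 per arm. The stated figure is reproduced.
- Exact power at 100 per arm, by binomial enumeration of the corrected test and counting rejections in favour of eslicarbazepine acetate (ESL): 80.9%.

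**Step 5. Illustration of size.** The documents give no re-stroke rate. Assume that a share s of non-failures in each arm is switched to failure: p′ = p + (1 − p)·s. Both pairs of rates are shown because the SAP describes 26% and 8% as already including missing data.

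| s (assumed) | Exact power, 29.7% vs 12.6% | Exact power, 26% vs 8% |
|---|---|---|
| 0 | 80.9% | 90.9% |
| 0.5% | 79.9% | 90.0% |
| 1% | 78.9% | 89.0% |
| 2% | 76.9% | 87.1% |

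At s = 1% in the first pair, extra failures per 100 are 70.3 × 0.01 = 0.70 on placebo and 87.4 × 0.01 = 0.87 on ESL. The risk difference becomes 0.99 × 17.1 = 16.9 points.

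**Step 6. One patient.** With 100 per arm, failures a (placebo) and b (ESL), χ² = 200·(|a(100 − b) − b(100 − a)| − 100)² / [(a + b)(200 − a − b)·100²].
- 30 vs 17: χ² = 4.00, p = 0.045. One more ESL failure, 30 vs 18: χ² = 3.32, p = 0.069.
- 30 vs 13: χ² = 7.58, p = 0.006. One more ESL failure, 30 vs 14: χ² = 6.56, p = 0.010.

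A single patient matters only close to the threshold.

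**The case against.** **Intent.** The protocol wording is an exemption, so the SAP rule was probably meant for strokes after 7 days. That is the natural reading of purpose, and it makes this a drafting gap rather than a wrong choice of analysis. The gap remains, because the SAP's own use of the term points to the exempt group.

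**Precedence.** The SAP's introduction says that it amends the protocol's statistical considerations, so a difference between the two is not in itself an error. This stands, but the tension between 5.2.3 and 5.5.1 lies inside the SAP. The change is also not listed in SAP section 8.

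**Unseen text.** Of the protocol, only the synopsis and schedule with the 96-hour criteria are available. The full text, including Version 3.0, was not supplied and may contain a withdrawal rule that settles the matter.

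**Existing safeguards.** The failure table by category, the tipping point analysis and the US-only analysis would help to expose any effect.

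**The illustration.** The share s is assumed, 100 per arm was not reached, and adding s to the 29.7% and 12.6% rates supposes that re-stroke withdrawals fall outside the 5% missing-data allowance. All of this stands, so the power figures are not an estimate of harm.

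**Conclusion.** The point holds as a minor one. SAP 5.5.1 needs a 7-day limit. Without it the text scores as failures those patients who have a re-stroke after randomisation and within 7 days of the primary stroke, and who are then observed without a US to the end of the window. How many there are is unknown and may be zero. Any effect is probably small.

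Four stronger readings might be inferred, and the documents do not support them:
- That every re-stroke, whenever it occurs, becomes a primary failure. The first-event rule and the Day 182 limit exclude re-strokes after a US or after the window.
- That the rule certainly gives withdrawal dates before randomisation. SAP 5.1.1 and 5.2.3 together suggest that pre-enrolment re-strokes fall outside it, although 5.5.1 does not say so.
- That the multiple imputation coding is left open for a patient with an early re-stroke and a later US. The first-event rule largely settles it as missing.
- That the comparison is biased between arms. Nothing supplied shows that early re-strokes differ by arm, and the illustration uses the same share in both.

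**What to change.** Before unblinding, reconcile the re-stroke definition in the protocol synopsis with SAP 5.2.3 and 5.5.1:
- Limit the 5.5.1 analysis rule to a new stroke more than 7 days after the primary stroke.
- State that patients with a further stroke within 7 days, including one before enrolment, are analysed by their observed outcome, and that an observed US is not overridden.
- Apply the same condition in 5.5.1.1 (multiple imputation and tipping point) and 5.5.2.1.
- List the rule in SAP section 8.

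The cost is one sentence on the rule, one line in section 8 and one date condition in the derivation. The date and time of the primary stroke are collected (SAP 5.2.2), and the rule already uses the re-stroke date. The planned sample size is unchanged, since re-stroke is not a named input to it. The change concerns the analysis rule only and leaves the SAP's handling of strokes after 7 days as it is.
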